## **4 Change to protocol specified analyses**

None.

## 6 Appendix

### 6.1 Imputation rules

#### 6.1.1 AE, CM date imputation

**Table 6-1 Imputation of start dates (AE, CM)**

Missing Element	Rule
day, month, and year	

• No imputation will be done for completely missing dates

day, month	

• If available year = year of study treatment start date then

◦ If stop date contains a full date and stop date is earlier than study treatment start date then set start date = 01JanYYYY

◦ Else set start date = study treatment start date.

• If available year > year of study treatment start date then 01JanYYYY

• If available year < year of study treatment start date then 01JulYYYY

day	

• If available month and year = month and year of study treatment start date then

◦ If stop date contains a full date and stop date is earlier than study treatment start date then set start date= 01MONYYYY.

◦ Else set start date = study treatment start date.

• If available month and year > month and year of study treatment start date then 01MONYYYY

• If available month and year < month year of study treatment start date then 15MONYYYY

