10.5.3.2 Adverse events (AEs)

Summary tables for adverse events (AEs) will include only AEs that started or worsened during the on-treatment period, the **treatment-emergent** AEs.

The incidence of treatment-emergent adverse events (new or worsening from baseline) will be summarized by system organ class, preferred term, severity (based on CTCAE grades), type of AE, relation to study treatment, periods and regimens as specified above and overall. AEs with different starts dates in different periods will be counted within each period.

AEs leading to discontinuation, serious AEs (SAE) and non-SAEs during the on-treatment period will be tabulated by type of AE.

All deaths (on-treatment and post-treatment) reportable as SAEs and non-fatal SAEs will be listed by patient and tabulated by type of AE.

All AEs, deaths and SAEs (including those from the pre and post-treatment periods) will be listed and those collected during the pre-treatment and post-treatment period will be flagged.

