#### 2.1.1 General definitions

The overall observation period is divided into the following **mutually exclusive** periods:

1. **Pre-treatment:** from day of patient's informed consent to the day before first dose of midostaurin

2. **On-treatment:** from start date of midostaurin to last date of study treatment + 30 days.

Further details provided in [Section 2.1.3](#).

On-treatment includes 3 mutually exclusive periods:

- a. **Induction** period: From day of first dose of midostaurin to the day before start of consolidation period (i.e. end of induction phase plus any rest/recovery days).  
Up to 2 cycles (28 days of treatment/cycle and a recovery period)
- b. **Consolidation** period: From day of first dose of study treatment in consolidation phase to the day before start of maintenance (i.e. end of consolidation phase plus any rest/recovery days).  
Up to 4 cycles (28 days of treatment/cycle and a recovery period)
- c. **Maintenance** period: From day of first dose of midostaurin in the maintenance phase to the date of last dose of midostaurin + 30 days.  
Up to 12 cycles (28 days of treatment/cycle)

It is noted that if a patient permanently discontinues study treatment during any of these periods, on-treatment is considered until the date of last dose of study treatment + 30 days (unless patient withdraws study informed consent or dies before then, then it is till the withdrawal/death date)

3. **Post-treatment:** from last date of study treatment + 31 days to end of study

Each period will contain all patients who entered that period (incl. withdrawal, drop-outs etc.)

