### **Date of first administration of study treatment**

The date of first administration of study treatment (will be midostaurin for all patients) is derived as the first date when a nonzero dose of any component of study treatment is administered. It is derived by period (induction, consolidation, maintenance) and overall.

For example, if the 1st dose of midostaurin is taken on 08-Feb-2016, and 1st dose of a combination partner (e.g. cytarabine), is taken on 01-Feb-2016, then the date of first administration of study treatment is 01-Feb-2016. The date of first administration of study treatment is also referred to as ***start date of study treatment***.

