#### **2.1.3 On-treatment assessment/event**

The definition of on-treatment is given below, depending on the context.

For safety summary tables (over the entire duration of the study) an on-treatment AE is defined as any AE reported in the following time interval (including the lower and upper limits):

- <date of first administration of midostaurin; date of last administration of study treatment + 30 days>

This corresponds to the definition of treatment-emergent AEs given in the protocol, i.e. AEs which are newly reported or worsening from baseline.

An on-treatment assessment is defined as any assessment performed after the date of first administration of midostaurin (except for assessments specified to be collected post-dose on that day), i.e. assessments performed in the following time interval (including the lower and upper limits):

- <date of first administration of midostaurin + 1; date of last administration of study treatment + 30 days>

For patients whose last date of study treatment is missing, on-treatment assessments/events include any assessment/event present in the database occurring after the start date of study treatment.

Listings will contain all data, flagging assessments/events outside of the on-treatment period where applicable.

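### SAP Table 6-1 ties partly missing AE start dates to a study treatment start that the SAP defines in two conflicting ways, one of which moves on-treatment AEs out of the safety tables

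*SAP*

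**What the plan says.** SAP Table 6-1 covers AE and concomitant-medication start dates with the day, or the day and month, missing. If the known month (or year) equals that of the anchor, and no full stop date falls before the anchor, the rule is "Else set start date = study treatment start date". If the known month or year is later than the anchor's, the first day of that month or year is used.

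SAP 2.1.1 (Date of first administration of study treatment) defines the anchor. A parenthesis says it "will be midostaurin for all patients". The same sentence derives it as the earliest non-zero dose among all components, and the worked example has cytarabine on 1 February and midostaurin on 8 February 2016, "then the date of first administration of study treatment is 01-Feb-2016". The preceding definition of study treatment includes cytarabine and the anthracycline.

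The on-treatment period uses a different term: it runs "from start date of midostaurin to last date of study treatment + 30 days". SAP 2.1.3 sets the AE window as "<date of first administration of midostaurin; date of last administration of study treatment + 30 days>", limits included. Protocol 10.5.3.2 adds the consequence: "Summary tables for adverse events (AEs) will include only AEs that started or worsened during the on-treatment period".

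**The concern.** The anchor for imputation and the opening of the AE window need to be the same date, or imputation can move an event across the boundary. If the anchor is the first chemotherapy dose, it normally precedes the window, because midostaurin starts on Day 8 of a cycle whose chemotherapy begins on Day 1 (Protocol 6.1, 6.5.2). An AE that truly began after midostaurin, but is recorded only to that month, is then set to a pre-treatment date. It drops out of the summary tables and remains only as a flagged listing record.

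The primary endpoint consists of proportions read from those tables. The exposed rows are patients with any AE, grade 3 and 4 AEs, SAEs and AEs leading to discontinuation. I make no claim about the death count. Two programmers who follow the SAP faithfully could produce different primary tables.

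The same ambiguity recurs twice. The study-day paragraph of SAP 2.1.1 names both midostaurin and study treatment as its reference, which affects listings only. The rule in SAP 2.1.3 for a missing last dose date says "on-treatment assessments/events include any assessment/event present in the database occurring after the start date of study treatment".

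**Working it through.** **Inputs.** Let *d* be the first midostaurin dose, which is the lower limit of the AE window (SAP 2.1.3). Let *g* be the number of days from the earliest counted chemotherapy dose to *d*; it is 7 in the SAP's example. The component anchor is *a* = *d* − *g*. The imputation rule is Table 6-1, for AEs with no full stop date before the anchor. A stop date cannot rescue a true on-treatment AE, because it is never earlier than *a*.

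**The SAP's own example.** The earlier of 1 and 8 February 2016 is 1 February, which matches the stated date. An AE recorded as February 2016 that truly began on any of the 22 days from 8 to 29 February is imputed to 1 February, 7 days before the window. With midostaurin as anchor it becomes 8 February, the first day of the window. An AE recorded as March 2016 becomes 1 March under the component anchor and is not lost.

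**All start dates.** Take an AE known only to the month of *d*, with *g* ≥ 1.
- If *a* is in the same month, the imputed date is *d* − *g*, which is before *d*.
- If *a* is in the previous month, the imputed date is the 1st of *d*'s month, which is before *d* unless *d* is itself the 1st.

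So the AE is lost unless *d* is the 1st of a month, whatever *g* is from 1 to 7. Four consecutive years have 1,461 days and 48 firsts of the month.

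| Precision of AE start | Imputed before window, component anchor | Midostaurin anchor, or *g* = 0 |
|---|---|---|
| Month and year | (1,461 − 48)/1,461 = 1,413/1,461 = 96.7% | 0% |
| Year only | (1,461 − 4)/1,461 = 1,457/1,461 = 99.7% | 0% |

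**Share of day-missing AEs lost.** Assume start dates and onset are uniform. The days at risk run from *d* to the end of its month, and are zero when *d* is the 1st. Their mean is (16 × 435 + 28 × 465 + 3 × 378 + 406)/1,461 = 21,520/1,461 = 14.73 days, from 16 thirty-day months, 28 thirty-one-day months, three Februaries of 28 days and one of 29.
- Onset in the first 21 midostaurin days (Days 8–28 of cycle 1), days at risk capped at 21: 19,593/1,461 = 13.41; 13.41/21 = 64%.
- First 51 days (21 + 30): 14.73/51 = 29%.
- 571 days (18 months = 548, less 7, plus 30): 14.73/571 = 2.6%.

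**Reverse error with the midostaurin anchor.** An AE after consent but before midostaurin, with the day missing and no full stop date before midostaurin, is imputed to *d* when it shares *d*'s month. For onset uniform over the *c* days before *d*, the share is 1 − (48/1,461) × (*c* + 1)/2. That is 96.7% for *c* = 1 and 86.9% for *c* = 7.

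**The case against.** The best case for the plan is that the midostaurin reading is available and natural. Most other AE boundaries use midostaurin. Protocol 7.1.2.3 collects the Day 1–7 chemotherapy as baseline information. The SAP derives the start date by period as well as overall, so its example could describe a consolidation cycle, with the parenthesis describing the overall start. But the example names no period. Even on that reading, any counted chemotherapy dose before midostaurin makes the overall derivation contradict the parenthesis. Table 6-1 also does not use the midostaurin term that the on-treatment period uses.

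SAP 2.1.1 limits study drug to use after consent, and consent may fall anywhere from Day 1 to Day 7 (Protocol 7.1.2). This stands as a limit: a 5+2 patient who consents on Day 6 or 7 has no counted chemotherapy before midostaurin and loses nothing. A gap of one day is enough for everyone else, and the exposed fraction of patients is unknown.

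The 96.7% and 99.7% are shares of calendar start dates, not of AEs. That is correct. Over a full course the share of day-missing AEs lost is 2.6%. On the SAP 2.1.6 maximum of 25 months, it is 14.73/(25 × 30.4375 − 7) = 14.73/754 = 2.0%.

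Other mitigations also stand. Start and end dates are sought for each AE, and a worsening, or an improvement from grade 3 or 4, gets a new dated entry (Protocol 8.1.1). Missing values are queried (Protocol 9.4). SAP section 1 leaves derivations to a programming document that is not public and may settle the point. None of this corrects the SAP text.

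Protocol 10.4.3 rules out imputation of missing data altogether. That does not defend Table 6-1; it is a further inconsistency to resolve.

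**Conclusion.** The concern holds and should be fixed. SAP 2.1.1 defines study treatment start in two ways that disagree for every patient with a counted chemotherapy dose before midostaurin, and Table 6-1 relies on that date. Following the derivation and example undercounts treatment-emergent AEs; following the parenthesis does not.

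The figures rest on uniform start dates, on uniform onset for the 64%, 29% and 2.6%, and on at least one counted chemotherapy dose before midostaurin. Nothing is lost if midostaurin began on the 1st of the month (1 January for year-only dates). AEs known to a later month, or a later year for year-only dates, are unaffected.

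The effect on the primary proportions cannot be sized, because the number of partially dated AEs is not given. A patient leaves a row only if no other AE qualifies there, so the overall AE proportion is probably insensitive; less common categories have less protection. The effect may be small.

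**What to change.** - In Table 6-1, for AEs, name the start date of midostaurin as the anchor. State separately which anchor applies to concomitant medications, since the table governs both.
- Use the same term in the study-day reference sentence of SAP 2.1.1 and in the missing-last-dose rule of SAP 2.1.3.
- In the definition of study treatment start, delete the parenthesis and keep the component derivation. The consolidation period needs it ("From day of first dose of study treatment in consolidation phase"), and so does the exposure rule in SAP 2.5.2.
- Report how many AEs change on-treatment status between the two anchors. This sizes the issue in either direction.

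The cost is a few words in four places of the SAP, one reference variable in the programs and one small count; no new data are needed. The latest SAP version is dated after database lock, so the change should be recorded as such. The drawback is that some AEs with onset after consent but before midostaurin, and only a partial date, will count as on-treatment. The count makes that visible.

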**Table 6-2 Imputation of end dates (AE, CM)**

Missing Element	Rule (*=last treatment date plus 30 days not > (death date, cut-off date, withdrawal of consent date))
day, month, and year	

• Completely missing end dates (incl. ongoing events) will be imputed by the end date of the on-treatment period*

day, month	

• If partial end date contains year only, set end date = earliest of 31DecYYYY or end date of the on-treatment period *

day	

• If partial end date contains month and year, set end date = earliest of last day of the month or end date of the on-treatment period*

In the case of the imputed end date is before than start date, then the end date will be imputed equals to start date.

Any AEs and ConMeds with partial/missing dates will be displayed as such in the data listings.

Any AEs and ConMeds which are continuing as per data cut-off will be shown as 'ongoing' rather than an imputed end date provided.

### **6.1.2 Prior therapies date imputation**

Missing day is defaulted to the 15th of the month and missing month and day is defaulted to 01-Jan for start and end dates in ZT domain.

### **6.2 Laboratory parameters derivations**

CTC grading for blood differentials is based on absolute values. However, this data may not be reported as absolute counts but rather as percentage of WBC.

If laboratory values are provided as ‘<X’ (i.e. below limit of detection) or ‘>X’, prior to conversion of laboratory values to SI unit, these numeric values are set to X.

The following rules will be applied to derive the WBC differential counts when only percentages are available for a xxx differential

$$\text{xxx count} = (\text{WBC count}) * (\text{xxx \%value} / 100)$$

Further derivation of laboratory parameters might be required for CTCAE grading. For instance, corrected calcium can be derived using the reported total calcium value and albumin at the same assessment using the following formula:

$$\text{Corrected Calcium (mg/dL)} = \text{Calcium (mg/dL)} - 0.8 [\text{Albumin (g/dL)} - 4]$$

In order to apply the above formula, albumin values in g/L will be converted to g/dL by multiplying by 0.1, calcium values in mmol/L will be converted to mg/dL by dividing by 0.2495. For calculation of laboratory CTC grades 0 and 1, the normal range for derived corrected calcium is set to the same limits (in mg/dL) as for calcium.

For missing Blood Urea Nitrogen (BUN) or urea values the following formulae will be applied:

$$\text{Urea (mg/dL)} = \text{BUN (mg/dL)} / 0.357$$

$$\text{BUN (mg/dL)} = \text{Urea (mg/dL)} / 2.1428$$

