7.2.2.5 Laboratory evaluations

Laboratory evaluations must be performed according to the [Table 7-1](#). Analyses and assessments are to be done locally and results transcribed to the eCRF. When abnormal laboratory values or test results constitute an adverse event (i.e., induces clinical signs/symptoms or requires therapy), they must be recorded on the Adverse Events eCRF.

All laboratory samples must be drawn **PRIOR** to the first dose of midostaurin.

All other laboratory evaluations should be performed when justified for the assessment of a treatment related AE or SAE and at physician discretion.

All efforts should be made to collect the labs prior to dosing. Fasting is not required.

If administration of midostaurin is interrupted due to \geq Grade 3 non-hematologic laboratory parameters, refer to [Section 6.3](#), for instructions.

The following laboratory assessment will be done by the local laboratory:

Table 7-3 Local clinical laboratory parameters collection plan

Test Category	Test Name
Hematology	Hemoglobin, Platelets, Red blood cells, White blood cells, Differential (Basophils, Eosinophils, Lymphocytes, Monocytes, Neutrophils, Bands)
Chemistry	Albumin, Alkaline phosphatase, ALT, AST, Lactate dehydrogenase (LDH), Calcium, Magnesium, Phosphorus, Sodium, Potassium, Creatinine, Creatine kinase, Direct Bilirubin, Total Bilirubin, Total Cholesterol, Blood Urea Nitrogen (BUN) or Urea, Uric Acid Amylase, Lipase, Glucose (fasting) or Glucose (non fasting)
Urinalysis	Macroscopic Panel (Dipstick) (Color, Bilirubin, Blood, Glucose, Ketones, Leukocytes esterase, Nitrite, pH, Protein, Specific Gravity, Urobilinogen)
Coagulation	International normalized ratio [INR]), Activated partial thromboplastin time or Activated thromboplastin time %
Pregnancy Test	When effective contraception is required pregnancy testing is mandated at screening and/or pre-dose and at the end of the trial. A serum pregnancy test should be performed; while at the end of trial urinary pregnancy tests are sufficient.
Note: All efforts should be made to collect the labs prior to dosing. Fasting is not required.	

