## 1 Introduction

This statistical analysis plan (SAP) provides detailed statistical methodology for the analyses of data which will be used for preparation of the PKC412A2408 clinical study report (CSR) and is based on the study protocol Amendment 1, dated 26-Mar-2018. At the time of this amendment, enrollement was completed with 301 patients.

The shells for the in-text tables and figures as well as the post-text tables, figures and listings (TFLs) are in the TFL shells document. Programming specifications for datasets, including derivation of variables, are given in the programming data specifications (PDS) document.

All data will be analyzed by Novartis using Novartis clinical data standards (NCDS). Analysis data sets and statistical outputs will be produced using the SAS system Version 9.4 or higher (UNIX environment) in the global programming & statistical (GPS) environment.

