#### **2.9.3 Laboratory data**

Laboratory values are converted to the international system of units (SI). CTCAE Grade 0 will be assigned for all non-missing values not graded as 1 or higher. Grade 5 will not be used. For laboratory results where grades are not defined by CTCAE v4.03, results will be categorized as low/normal/high based on laboratory normal ranges.

The following summaries will be generated separately for key hematology and biochemistry by period and overall for the safety set:

- Shift tables by grade (or low/normal/high if grades not available) to compare baseline to the worst on-treatment value:
  - Hematology: Neutrophils (absolute) and platelets
  - Chemistry: Creatinine, total bilirubin, aspartate aminotransferase (AST), alanine aminotransferase (ALT) and alkaline phosphatase

Listing of all laboratory data (including urinalysis, coagulation, thyroid panel, pregnancy test etc.) will be provided with the corresponding CTCAE grades, if applicable, and the classifications relative to the laboratory normal ranges. Records outside of on-treatment period will be flagged.

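### The SAP's two formulas for filling in a missing BUN or urea value contradict each other by a factor of 1.307

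*SAP*

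**What the plan says.** Protocol Table 7-3 (section 7.2.2.5) lists the chemistry test as "Blood Urea Nitrogen (BUN) or Urea", so a site may report either one. SAP section 6.2 then states: "For missing Blood Urea Nitrogen (BUN) or urea values the following formulae will be applied". Two formulas follow (the stray characters in the quotes are typesetting code):

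- urea from BUN: "Urea (mg/dL)} = \text{BUN (mg/dL)} / 0.357"
- BUN from urea: "BUN (mg/dL)} = \text{Urea (mg/dL)} / 2.1428"

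Both sides of both formulas are labelled mg/dL. No condition, population or other unit is given that would call for two different ratios. According to the SAP document history, the rule was added in the January 2020 update.

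For corrected calcium, the same section says that "the normal range for derived corrected calcium is set to the same limits (in mg/dL) as for calcium". It has no matching sentence for derived urea or BUN.

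SAP section 2.9.3 plans a listing of all laboratory data with classification against laboratory normal ranges. Its chemistry shift tables cover "Creatinine, total bilirubin, aspartate aminotransferase (AST), alanine aminotransferase (ALT) and alkaline phosphatase", so neither BUN nor urea is included.

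**The concern.** Converting between BUN and urea in the same unit needs a single constant: multiply by it in one direction, divide by it in the other. The SAP uses two constants that do not match, so at least one line gives wrong values if programmed as printed.

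Sites may report either test, so the data would mix measured and derived values of the same analyte on different scales. If the first line is the faulty one, urea derived at a BUN-reporting site could not be compared with urea measured elsewhere. If derived urea is also set against a urea normal range, some values would carry the wrong low/normal/high flag. The section gives no range rule for derived urea, so such flags are possible but not certain.

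**Working it through.** **Inputs (SAP section 6.2)**
- Divisor from BUN to urea: 0.357
- Divisor from urea to BUN: 2.1428

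**Are the formulas inverses?** With equal units, y = x/a and x = y/b are inverses only if a x b = 1.
- 0.357 x 2.1428 = 0.765, not 1.
- First formula: urea = BUN x (1/0.357) = BUN x 2.8011.
- Second formula, inverted: urea = BUN x 2.1428.
- Mismatch: 2.8011 / 2.1428 = 1.307.

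**Could rounding explain it?** Move each constant to the limits of its printed precision.
- Lowest: (1/0.3575) / 2.14285 = 1.305.
- Highest: (1/0.3565) / 2.14275 = 1.309.
- Rounding does not explain the gap.

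**Example**

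| BUN (mg/dL) | Urea by first formula | Urea by inverse of second | First result put through second formula |
|---|---|---|---|
| 10 | 28.01 | 21.43 | 13.07 |
| 20 | 56.02 | 42.86 | 26.14 |

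At BUN 20 mg/dL the two urea values differ by 56.02 - 42.86 = about 13.2 mg/dL. The last column only demonstrates the inconsistency, because the plan never converts a derived value back.

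**Which line is wrong?** This step rests on an assumption from outside the documents, namely standard atomic masses.
- Urea 60.056, its two nitrogens 28.014: ratio 60.056 / 28.014 = 2.144.
- 2.1428 is within 0.1% of this; 2.8011 is about 31% above it.
- 10 / 28.014 = 0.357. On the same assumption, 0.357 is the multiplier from BUN in mg/dL to urea in mmol/L. A mixed-unit constant may therefore have been put into a mg/dL formula.
- Relabelling urea as mmol/L does not rescue the printed line. That conversion multiplies by 0.357, whereas the line divides by it, so the result would be wrong by 1 / (0.357 x 0.357) = about 7.8-fold.

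**Possible effect on flags.** This assumes that the first line is the faulty one, that it was programmed as printed, and that derived urea is compared with a urea normal range.
- Derived urea = 1.307 x true urea, and 1 / 1.307 = 0.765.
- True values between about 76.5% and 100% of the upper limit would be listed as high.
- True values between about 76.5% and 100% of the lower limit would be listed as normal.
- Other values would keep the correct flag.

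**The case against.** The contradiction itself is not open to dispute. The case on the other side concerns its cause and its reach.

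- **The documents do not say which line is wrong.** This stands. If 0.357 were right, the second line would be at fault and derived BUN would be the affected quantity. The choice depends on the atomic-mass assumption.
- **It may be a unit misprint.** SAP section 2.9.3 converts laboratory values to SI units, so a urea value in mmol/L is plausible, and correct code would leave only a printing error. This is possible and bears on the fix. It does not make the printed line right, because the operator would be wrong as well as the unit.
- **The code may be right.** SAP section 1 says: "Programming specifications for datasets, including derivation of variables, are given in the programming data specifications (PDS) document". That document is not available here, so whether any output is wrong cannot be determined.
- **The flag error is speculative.** Nothing shows that a site reporting BUN also supplies a urea range. The bands above are illustrative.
- **Little depends on these values.** Protocol Table 7-1 schedules chemistry at screening; later tests are done when justified by a treatment-related AE or SAE and at the physician's discretion. Few derived values after baseline are therefore likely. Laboratory adverse events are recorded by the investigator from local results (Protocol sections 7.2.2.5 and 8.1.2), not from derived urea. This stands and keeps the point minor.

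**Conclusion.** The concern holds as a minor arithmetic error. It is certain from SAP section 6.2 alone that the two formulas disagree by a factor of 1.307. That the first line is the faulty one, with derived urea about 31% too high, rests on the atomic-mass assumption and on the line being programmed as printed. On that reading measured BUN is unaffected, and the error is confined to derived urea in the laboratory data and listings. The shift tables, the adverse-event endpoint and the CR/CRi rate do not use it.

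**What to change.** 1. Reconcile the two lines in SAP section 6.2, including their units. Under the mass-ratio assumption, the first becomes urea (mg/dL) = BUN (mg/dL) x 2.1428, and the second stays as it is. If urea in mmol/L was intended, both the unit and the operator need correcting: urea (mmol/L) = BUN (mg/dL) x 0.357.
2. Add a sentence stating which normal range, if any, applies to derived urea, as is already done for corrected calcium.
3. Check the programming data specifications and the code against the corrected formula. Re-run derived urea and any range flags only if the printed formula was used.

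The cost is one corrected line, one added sentence and a check of one derivation.
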